## Security Measures

Patients will be evaluated for early detection of side effects, particularly in relation to increases in calcemia and fosfatemia. Both calcium and phosphorous will be measured monthly.

If it were necessary to open the blinding, it will be requested from the person in charge of assigning the medication at the pharmacy.

#### Calculation of sample size

It was estimated, by using free access epidemiological calculator Open Epi (to be found at <http://www.openepi.com/v37/SampleSize/SSCohort.htm>), that necessary sample size to show a IPTH decrease of 20% in 35% of patients in the group treated (information we found in a previous observational study) is 102, and assuming a 15% loss of follow-up, a sample size of 120 was decided on. This size is more demanding than the 50 patients needed to demonstrate the correction of 25VD in 50% of patients.

#### Expected Results

Primary end point: A difference in the percentage of patients normalizing levels of 25VD of at least 45% of the group treated vs placebo.

Percentage of patients of at least 30% in the group treated vs placebo presenting a decrease of 20% from previous levels of IPTH.

Secondary end point: Percentage of patients with an increase in Hb or a decrease in resistance to erythropoietin

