## SUMMARY

Introduction. Vitamin D regulates mineral metabolism, playing a crucial role in maintaining adequate bone density. Immunomodulatory, cardioprotective and

Version December 7th, 2015

antiproliferative effects have been described recently. Its deficiency has been associated with diabetes, cancer and increased mortality. 25OH vitamin D (25VD) is stable (with a half-life of over 2 weeks) and suitable for the evaluation of vitamin D sufficiency. It has been found that levels of 25VD are inversely related to those of the parathyroid hormone (iPTH), and its supplementation has been associated with a decrease in levels of iPTH in patients with Chronic Kidney Disease, although these results have not been uniform in patients on hemodialysis (HD). The usual treatment for secondary hyperparathyroidism in HD with active and analogous forms of vitamin D increases the risk of hyperphosphatemia and vascular calcifications.

The aim of the study is to evaluate whether cholecalciferol supplementation for a period of 12 weeks can normalize decreased levels of 25VD and reduce increased iPTH in HD patients with a vitamin D deficiency. Secondary aims: to evaluate decrease in inflammation, anemia or use of erythropoietin (epo).

**Design.** Randomized, double blind clinical trial in two arms of HD patients with 25VD deficiency and secondary hyperparathyroidism, one arm to be treated with cholecalciferol supplementation and the other with a placebo, for a period of 12 weeks.

**Population.** Patients over 18 years of age on HD for more than 3 months and levels of 25VD < 30 ng / ml and iPTH >300 ng/ml , who sign a consent form. Patients will be recruited over a period of one year. Once their consent has been obtained, iPTH and 25VD levels will be measured. Randomization will be achieved by using a table of random numbers at the pharmacy, and neither doctors nor patients will know which group they have been assigned to.

Treatment. Supplementation will consist of one 5000 IU 25VD tablet or placebo during dialysis for a period of 12 weeks.

Monthly monitoring will include: hemoglobin (g/dl), Calcium (mg/dl), Phosphorous (mg/dl), iPTH (ng/ml), epo dose (IU/kg/week), epo resistance (IU/kg/week/g Hb).

At the beginning and end of the study the following will be measured: alkaline Phosphatase (IU/ml), PCR (mg/L), 25VD (ng/ml), ferritin (ng/ml) and transferrin saturation, quality of life (SF36).

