During the study, doses of calcitriol or paricalcitol will not be modified.

The study will be discontinued if calcemia  $\geq$  10.5 mg/dL is detected on two occasions.

Size of sample is estimated at 120 patients for a iPTH decrease of 20% in 35% of patients in group treated (assuming 15% follow-up losses). Analysis will be done for Intention to treat for the primary outcome.

Ethical aspects: Authorization has been obtained from the Ethics Committee of the institution as regards Good Clinical Practices, Helsinki Declaration and national regulations. The test will be registered with Cochrane and the Ministry of Public Health.

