### POPULATION

Criteria for inclusion: Age 18 or over, signed informed consent form, CKD with regular dialysis treatment for at least 3 months, levels of 25VD < 30 ng / ml and iPTH >300 ng/ml, stable doses of calcitriol or paricalcitol over the last 30 days.

Criteria for exclusion: Congestive heart failure class III or IV or unstable angina

or myocardial infarction or stroke during the previous 3 months, active malignant neoplasm, use of any trial medication, life expectancy lower than 6 months, corrected calcemia  $\geq 10.5$  in the 2 months prior to recruitment, intake of cholecalciferol or ergocalciferol in the 2 months prior to recruitment, prospective move to another city or transfer to PD in the following 6 months.

Patient recruitment. Patients will be recruited over a one-year period when the study will be explained to them, and samples will be taken to assess whether they fulfill the criteria for inclusion in the trial. Once iPTH and 25VD testing has taken place, eligible participants will be requested to sign an informed consent form, and will be told that they will be treated either with cholecalciferol or a placebo. They will be assigned to one of the arms using a table of random numbers at the pharmacy of the institution, stratified in two subgroups according to vitamin D levels: below 15 ng/ml or between 15 and 29.

Randomization. Once approval has been received from the Ethics in Research Committee and the consent form has been signed, patients will be assigned to one arm by using a table of random numbers, according to a number from 0 to 9 which will be drawn at random at the time the patient is included. For purposes of randomization, one fixed number will be skipped from the starting point which is only known by the person who does the randomization at the pharmacy, using a starting point selected initially on the table. Notification of the arm allocated will arrive in sealed envelopes with the medication to be taken (either cholecalciferol or the placebo) which will be administered orally during dialysis.

The laboratory that prepares the medication and the placebo will send them to the pharmacy labelled as medication A and B. Then the pharmacy of the

institution will send the tablets to the patient, neither the doctors nor the patient knowing what arm he has been assigned to. The medication will be administered by the nurse during dialysis.

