It will not be necessary to make changes to the dietary intake of vitamin D as dairy products, which are the main source of dietary vitamin D, are strictly limited in the diets of these patients.

Treatment: Supplementation will consist of one 5000 IU tablet of 25VD or placebo taken during dialysis for a period of 12 weeks. A nurse from the team will ensure access to the medication by being in permanent contact with the pharmacy. Monthly follow-up of the patients in the study will include evaluation of laboratory tests as well as normal clinical controls during dialysis (weight, arterial pressure and intra-dialysis hypotension events), and monthly report of dosage of erythropoietin (IU/kg/week) for the calculation of the index of resistance to erythropoietin (IU/kg/week / g of Hb).

Laboratory testing to be done monthly will include: hemoglobin (g/dl), Calcium (mg/dl), Phosphorous (mg/dl), and iPTH (ng/ml). At the beginning and at the end of the study the following will be measured: Alkaline Phosphatase (IU/ml), CRP (mg/L), ferritin (ng/ml), transferrin saturation, and 25VD (ng/ml).

The measuring of hemoglobin will be done by Siemens Healthcare Diagnostics' Advia 2120 haematological analyzer using the cyanmethemoglobin method modified without cyanide, with Siemens controls and calibrators. Dosing of vitamin D, iPTH and ferritin will be done by Siemens Healthcare Diagnostics' Advia Centaur XP analyzer using the chemiluminescence method, with BIORAD controls and Siemens calibrators.

Other measures will be taken as follows: for calcium, by the Arsenazo III endpoint method, for phosphorous, by the UV phosphomolibdate method, for alkaline phosphatase, by the kinetic technique of paranitrophenol phosphate, for iron, by the endpoint ferrocin method, for transferrin, by the immunoturbidimetric method maximized with PEG, and for reactive C Protein, by the immunoturbidimetric method maximized with latex. All of these will be done by Siemens Healthcare Diagnostics's Advia Chemistry 1800 autoanalyzer with BIORAD controls and Siemens calibrators.

Both prior to the start of the study and after it has ended, quality of life will be evaluated using SF36 auto-administered protocol.

During the 12 weeks of the study, doses of calcitriol or paracalcitol must not be modified. The study will be discontinued in those patients who present levels of calcemia  $\geq 10.5$  mg/dL on two occasions.

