Operational Definitions: 25VD levels are considered normal when above or equal to 30 ng/ml, and severe deficiency (SD-25VD) when below 10 ng/ml. Anemia is defined as presenting levels of Hb below 10g/dl or the need for epo. It is classified as mild anemia when patients have no anemia or require doses of epo below or equal to 2000 IU per week, and, failing this, very mild anemia. Ferritin is considered to be high when over 500 ng/ml. Measurements of all analytes will be done with Siemens equipment at the CASMU laboratory.

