### Statistics

Continuous variables with normal distribution will be compared using Student's test for independent or dependent samples as appropriate and will be presented as the mean  $\pm$  standard deviation. Categorical variables will be compared using Chi square test for paired or independent samples as appropriate

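### The anemia end point cuts Hb and epo resistance at zero change and leaves epo dose out of the Hb part, which costs power and makes the percentage hard to read

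*Protocol*

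**What the plan says.** Protocol, Expected Results, gives the secondary end point as "Percentage of patients with an increase in Hb or a decrease in resistance to erythropoietin". It attaches no minimum change to either part and no epo-dose condition to the Hb part.

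The Summary lists among the monthly variables "epo dose (IU/kg/week), epo resistance (IU/kg/week/g Hb"), and the Treatment paragraph under Population provides for a "monthly report of dosage of erythropoietin (IU/kg/week) for the calculation of the index of resistance to erythropoietin". The index is therefore epo dose divided by Hb.

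Only the active vitamin D drugs are held constant. The inclusion criteria ask for "stable doses of calcitriol or paricalcitol over the last 30 days", and the Treatment paragraph adds "During the 12 weeks of the study, doses of calcitriol or paracalcitol must not be modified"; the Summary says the same. No section says this of epo.

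The Operational Definitions count epo need as part of anemia: "Anemia is defined as presenting levels of Hb below 10g/dl or the need for epo". For the test, Statistics says "Categorical variables will be compared using Chi square test for paired or independent samples as appropriate". Student's test is kept for normally distributed continuous variables, so an end point fixed as a percentage falls under chi-square.

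**The concern.** Two features of the end point weaken it.

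- **The cut at zero.** An Hb change of +0.1 g/dL and one of +2 g/dL count alike. With no treatment effect, about half of the patients lie above zero by random variation alone. The size of the change, which is measured, is thrown away.
- **The dose-blind Hb part.** Hb can rise because the patient responds better to epo or because more epo was given. The index separates these two; a rise in Hb alone does not. If the two parts form one composite, a patient can succeed on Hb while the index gets worse.

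At stake are the power and the meaning of the only anemia result listed under Expected Results. The percentage mixes better epo response, higher epo dosing and random variation, and the reader cannot tell them apart.

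**Working it through.** The protocol attaches no figure to this end point, so there is none to reproduce. It gives no SDs and no frequency of epo dose changes either; the inputs in steps 2 to 4 are assumptions, apart from 51 per arm (half of the 102 under Calculation of sample size).

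**Step 1. Can a success have a worse index?** Index = epo dose / Hb.

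- Before: 100 / 10.0 = 10.0
- After: 130 / 10.3 = 12.6, which is 26% worse

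Hb rose, so on the composite reading the patient counts. This step needs no assumption about variability.

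**Step 2. How often could it happen?** Simulation without treatment effect, all patients on epo: SD of Hb change 0.8 to 1.2 g/dL, SD of log epo-dose change 0.2 to 0.4, correlation -0.5 to +0.5, mean baseline Hb 10.5 or 11.0.

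| Share of epo doses changed | Composite success by chance | Of these, index worse |
|---|---|---|
| none | 50% | 0% |
| 30% | 53-59% | 6-16% |
| half | 55-65% | 10-24% |
| all | 61-80% | 18-38% |

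On the two-end-point reading each part is met by about 50% by chance. If 30% of doses change, 7-19% of the patients whose Hb rose have a worse index.

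**Step 3. What does the cut at zero cost?** 51 per arm, two-sided 5%, true Hb difference 0.5 g/dL, SD of change 1.0.

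- t-test on Hb change: noncentrality = 0.5 / (1.0 × √(2/51)) = 2.52 on 100 degrees of freedom; power 71%.
- Percentage with any Hb rise: Φ(0.5/1.0) = 69.1% against 50%; exact binomial enumeration with the uncorrected chi-square test gives power 52%.

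The loss is about 18 points (70.6% less 52.5%). With SD 0.8 the pair is 88% and 70%; with SD 1.2 it is 55% and 40%. Adjusting for baseline raises the 71% to about 82% if the correlation between baseline and week 12 is 0.5.

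**Step 4. Does the 'or' cost more?** Same setting, log-dose SD 0.3, correlation -0.5 to +0.5. The dose effect applies to changed doses.

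| True effect | Doses changed | 'Or' percentage | Hb-only percentage |
|---|---|---|---|
| Hb +0.5, no dose effect | 30% | 44-45% | 52% |
| | half | 40-41% | 52% |
| | all | 29-35% | 52% |
| Hb +0.25, log dose -0.2 | 30% | 24-25% | 18-19% |
| | half | 29-30% | 18-19% |
| | all | 46-67% | 18-19% |
| Hb +0.5, log dose -0.2 | 30% | 54-56% | 52-53% |
| | half | 57-59% | 52-53% |
| | all | 66-84% | 52-53% |

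The sign changes: the 'or' loses power if only Hb improves and gains over the Hb-only percentage if epo dose also falls.

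**Step 5. Is a continuous comparison better?** In each scenario run, at least one of the two continuous comparisons beat the 'or' percentage. With Hb +0.5 and no dose effect it is Hb (71% against 44-45% if 30% of doses change). With Hb +0.25, log dose -0.2 and 30% of doses changed it is the log index (48-65% against 24-25%); Hb alone has 24% there.

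**The case against.** - **The reading is open.** The 'or' may name two end points, or may supply the index for patients on epo and Hb for those who are not. A reader might infer that the protocol certainly counts patients with worse resistance as successes; the text does not settle this. The objection stands: the worked example applies to the composite reading only.
- **The cost of the 'or' depends on the scenario.** A reader might infer from the first rows of step 4 that the 'or' always loses power. It does not. The stated aim is less anemia or less need for epo, and if dose falls too the 'or' gains over the Hb-only percentage. This stands in full.
- **The end point might seem to contradict the aim.** It does not: the aim uses the same 'or'.
- **The protocol already has much of the remedy.** Hb, epo dose and the index are recorded monthly and a t-test is named for continuous variables, so nothing bars such analyses, and time point and adjustment can be left to an SAP. This stands in part. The form of the end point, a percentage cut at zero, is fixed here, and an SAP that changed it would be changing the protocol's end point.
- **The sizes are assumed.** True. If few epo doses change, few composite successes have a worse index.

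**Conclusion.** The concern holds as a minor one. The protocol turns measured quantities into a percentage cut at zero, and the Hb part does not account for an epo dose that is free to vary. On the composite reading a patient with worse resistance can be a success; on the two-end-point reading what remains is the cut at zero and an Hb percentage without dose.

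The firmest figure is the loss from cutting Hb change at zero: about 71% to 52% power, given 51 per arm, a true gain of 0.5 g/dL and SD 1.0. No fixed further cost of the 'or' is claimed.

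Nor do the documents support a claim of bias. Both arms are judged by the same rule in a randomized, double-blind trial, so the comparison stays valid. The primary end points and the sample size of 102, raised to 120, are unaffected.

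**What to change.** Under Expected Results, replace the percentage by two separate week-12 comparisons between arms, each adjusted for its baseline value:

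1. the epo resistance index in patients on epo at baseline;
2. Hb in all patients, shown beside the change in epo dose.

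It is tempting to keep the percentage and merely refuse to count an Hb rise when the index worsened. This is not advised. For patients on epo that rule reduces to 'index fell', and if only Hb improves (+0.5, no dose effect) its power is 35-38%, 26-29% or 10-13% when 30%, half or all doses change, below the 'or' rule each time.

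The cost is wording only: no new data are needed and epo dosing is not touched. The downsides are two secondary results instead of one, an index comparison that leaves out patients not on epo (the Operational Definitions imply that there may be some), and low power for the index if only Hb changes (about 10-29% in unadjusted runs). That last point is why Hb has to be reported as well.

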#### Ethical Aspects

Authorization has been obtained from the Ethics Committee of the institution. The study will be carried out following Good Clinical Practices, the Helsinki Declaration and national and Mercosur regulations, according to the Ottawa Declaration.

The test will be registered in the Cochrane and WHO Clinical Trials Register, and authorization and registration will be requested from the Uruguayan Ministry of Public Health.

#### Data Analysis and Statistics

Reference demographic data will be collected related to: age, gender, race, cause of kidney disease, length of time on dialysis, presence of diabetes and use of active forms of vitamin D.

Clinical data will be taken from electronic medical records of dialysis (SISDIA): body weight, height, body mass index, monthly average of systolic and diastolic arterial pressure pre-dialysis, and monthly average percentage of inter-dialysis weight increase.

Both clinical information and laboratory data will be entered in a case report form (CRF) which will be attached as Annex 1.

Laboratory test data will be collected in Table 1 Schedule of measures.

TABLE I. SCHEDULE OF MEASURES

	Time 0	week 4	week 8	week 12	week 16
25VD					
iPTH					
Ca					
P					
Alkaline Phosphatase					
Hb					

CRP					
Ferritin					
Sat Transferrin					
SF36					
Mean SAP					
Mean DAP					
Mean inter-dialytic weight gain					
Number of hipotensive events					

The information obtained from patients' CRFs will be entered in a database which will be treated as confidential. Sensitive data will be kept confidential and patients' identity will remain anonymous during the whole procedure.

In order to ensure the quality of the information, all data entered will be checked by a second member of the research team prior to statistical analysis.

### Statistics

Continuous variables with normal distribution will be compared using Student's test for independent or dependent samples as appropriate and will be presented as the mean  $\pm$  standard deviation. Categorical variables will be compared using Chi square test for paired or independent samples as appropriate

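### The protocol randomises within two baseline 25VD strata but fixes a plain chi-square test that ignores them; a stratified test fits the design better, at a modest gain

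*Protocol*

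**What the plan says.** **Allocation.** In the Population section (patient recruitment), assignment is "stratified in two subgroups according to vitamin D levels: below 15 ng/ml or between 15 and 29" ng/ml. The randomisation paragraph of the same section gives the mechanism: "patients will be assigned to one arm by using a table of random numbers, according to a number from 0 to 9", the digit being drawn when the patient is included. It describes no blocks or other device that would hold the arms equal within a stratum.

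**Primary end points.** Under Expected Results both are percentages of responders. The first is "A difference in the percentage of patients normalizing levels of 25VD of at least 45% of the group treated vs placebo". The second is "Percentage of patients of at least 30% in the group treated vs placebo presenting a decrease of 20% from previous levels of IPTH".

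**Test.** The Statistics section has two sentences. The one that applies to responder outcomes reads "Categorical variables will be compared using Chi square test for paired or independent samples as appropriate". It names no stratified or adjusted test, and the protocol mentions no confidence interval.

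**The concern.** When randomisation is stratified on a factor, the primary comparison should normally use that factor. Here the factor is the baseline value of the first primary outcome. The Operational Definitions set normal 25VD at 30 ng/ml or more. A patient who starts below 15 ng/ml must therefore gain more than 15 to count as a responder, while a patient who starts at 15 to 29 needs a gain of 1 to 15. The chance of normalising probably differs between the strata.

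The plain chi-square treats that difference as noise. With arms balanced within strata, this overstates the standard error and makes the test conservative. With simple allocation, the arms can differ by chance in their share of low-25VD patients, and the plain test does not correct for it. The link between the stratum and the iPTH end point is less direct, so less is at stake there.

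**Working it through.** **1. The plan's own figures.** The Calculation of sample size section gives "necessary sample size to show a IPTH decrease of 20% in 35% of patients in the group treated" and says that it "is 102, and assuming a 15% loss of follow-up, a sample size of 120 was decided on". It also says "This size is more demanding than the 50 patients needed to demonstrate the correction of 25VD in 50% of patients". It does not state the placebo rate, alpha or power. Assume 10% on placebo, two-sided 5%, 80% power, 1:1 allocation and a continuity correction.

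- Formula: n = [1.96·√(2·p̄(1−p̄)) + 0.8416·√(p1(1−p1) + p2(1−p2))]² / d², where p̄ is the mean of p1 and p2 and d = p1 − p2. With the correction, n' = (n/4)·[1 + √(1 + 4/(n·d))]².
- iPTH, 35% v 10%: n = 42.6 and n' = 50.3, so 51 per arm, 102 in all. Then 102/0.85 = 120.
- 25VD, 50% v 10%: n = 19.4 and n' = 24.1, so 25 per arm, 50 in all.

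All three stated figures reproduce. A 10% placebo rate is therefore a reasonable working value. The 45-point target for 25VD against 50% treated would imply about 5%.

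**2. Assumptions for the strata.** 102 evaluable patients, half in each stratum. Stratum-specific rates are not in the documents, so several are tried. They are written lower stratum/upper stratum.

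**3. Type I error.** Simulated, two-sided 5%, 200,000 trials per setting, no continuity correction:

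| Null rates by stratum | Balanced within strata: chi-square v CMH | Simple allocation: chi-square v CMH |
|---|---|---|
| 25VD 1%/9% | 4.2% v 4.8% | 4.2% v 4.0% |
| 25VD 10%/50% | 3.0% v 4.9% | 5.0% v 4.9% |
| iPTH 7%/13% | 4.9% v 5.2% | 5.0% v 4.9% |

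The 4.2% and 4.0% under simple allocation reflect small expected counts, not the strata, since both tests show it. The 10%/50% null means that 30% normalise in both arms, well above the 5% to 10% placebo rate that the plan implies.

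**4. Chance imbalance under simple allocation.** The average error rate is about nominal, but a single trial can be unbalanced. Suppose 31 of 51 patients in one arm and 20 of 51 in the other are in the upper stratum, a gap of 11/51 = 21.6 points. With no treatment effect:

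- null 5%/25%: expected spurious difference 0.216 × 20 = 4.3 points; error rate about 8% for chi-square and 5% for CMH;
- null 10%/50%: 0.216 × 40 = 8.6 points; about 13% v 5%;
- null 1%/9%: 0.216 × 8 = 1.7 points; 5.5% v 3.6%.

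A gap of 20 points or more arises in about 4% of simply allocated trials of this size, and a gap of 10 points or more in about 30%.

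**5. Precision for 25VD, arms balanced within strata.** Half-width = 1.96·√(V/51). For 50% v 10%, unstratified V = 0.5·0.5 + 0.1·0.9 = 0.34, giving 16.0 points. Stratified V is the mean of p(1−p) over the strata, summed over arms:

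| Treated; placebo by stratum | V | Half-width | Extra patients the plain analysis needs |
|---|---|---|---|
| 35%/65%; 5%/15% | 0.315 | 15.4 | 0.34/0.315 − 1 = 8% |
| 25%/75%; 2%/18% | 0.271 | 14.3 | 0.34/0.271 − 1 = 25% |
| 15%/85%; 0%/20% | 0.2075 | 12.5 | 0.34/0.2075 − 1 = 64% |

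As information lost (1 − V/0.34), these are 7%, 20% and 39%. The last row is extreme.

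**6. Power, simple allocation.** 25VD, 50% treated against 5% or 10% placebo: above 99% with either test. iPTH, 35% v 10%, chi-square v CMH: 87.9% v 87.7% with strata weakly prognostic, 87.8% v 89.2% with strata strongly prognostic. If the stratum is unrelated to iPTH response, CMH costs about 0.5 point (87.8% v 87.3%).

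**The case against.** A reader might infer that the plain chi-square makes p values and intervals too conservative for both primary end points. The documents do not support that. Conservatism needs arms balanced within strata. The protocol says that allocation is stratified but describes only draws from a random-number table, and simple draws within each stratum do not balance the arms. Under that reading the two tests have about the same error rate. For iPTH the difference is negligible under either scheme. No interval is planned, so none is stated too wide. This part of the objection stands and limits the claim.

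The larger precision figures rest on extreme assumed stratum rates. That also stands; they mark the edge of a range and are not an expectation.

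A further objection is that the Statistics section is generic and that adjustment is commonly left to a statistical analysis plan, which is not shown and may name a stratified test. This stands in part. However, the protocol is not silent: it names a test for categorical outcomes, and that test omits the factor on which the protocol stratifies.

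**Conclusion.** The point holds as a minor mismatch between design and analysis. The stated test ignores the randomisation strata. If arms are balanced within strata, it is conservative for 25VD normalisation, slightly so at the placebo rates the plan implies (4.2% v 4.8%) and more so at higher common rates (3.0% v 4.9% at 10%/50%). If allocation is simple, as the text suggests, the average error rate is about nominal; what is lost is correction for chance imbalance and some precision. Type I error is not inflated on average to any material degree under either scheme.

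The trial's conclusions are unlikely to turn on this: 25VD power is above 99% either way, and iPTH changes by between a loss of about half a point and a gain of up to 2 points. These sizes assume 102 evaluable patients, 1:1 allocation, equal strata, a 5% to 10% placebo rate at the planned effect, and the stratum rates shown, none of which the protocol gives except the 102. The case for a stratified test does not depend on which reading of the allocation is right.

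**What to change.** In the Statistics section, state that both primary end points will be tested with a Cochran-Mantel-Haenszel test stratified by the randomisation stratum (25VD below 15; 15 to below 30 ng/ml). Report the Mantel-Haenszel risk difference with its 95% CI, and keep the plain chi-square as a sensitivity analysis. In the randomisation paragraph, state whether allocation is blocked within strata.

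The cost is about one sentence in each place. The stratum is known for every patient at entry, so no new data or patients are needed. The statistical downside is at most about 0.5 power point, if the stratum is unrelated to response and allocation is simple.
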